8.1.2 Planned Analysis

All randomized subjects who received study medication will be evaluated for safety. The efficacy analysis will be conducted on both the PP and the mITT subject populations. Two-sided hypothesis testing will be conducted for tests. Resulting p-values less than or equal to 0.05 will be considered

Protocol No: PRG-NY-15-003

statistically significant. No adjustments of p-values for multiple comparisons will be made. No interim analyses are planned. SAS software will be used for all data analyses and tabulations.

The treatment response will be summarized by treatment group for the end-of-treatment evaluation. The two primary efficacy endpoints will be the mean percent change from baseline to Week 12 in the inflammatory (papules and pustules) lesion counts AND the mean percent change from baseline to Week 12 in the non-inflammatory (open and closed) lesions.

8.1.3 Sample Size Considerations

8.1.4 Efficacy Measures and Analysis

Clinical endpoints

The primary efficacy measure will be the mean percent change from baseline to Week 12 in the inflammatory (papules and pustules) lesion counts AND the mean percent change from baseline to Week 12 in the non-inflammatory (open and closed) lesion counts. The secondary efficacy measure will be the proportion of subjects with clinical success on the Investigator's Global Assessment (IGA) at Week 12. Success is defined as an IGA score that is at least 2 grades less than the baseline assessment.

Equivalent efficacy

Protocol No: PRG-NY-15-003

For the mean percent reduction from baseline in the inflammatory and non-inflammatory lesion counts, the Test treatment will be considered to be therapeutically equivalent to the Reference treatment if the 90% confidence interval on the Test-to-Reference ratio of means, calculated by Fieller's Method, falls within the interval 0.80 to 1.25. The treatment means and estimate of residual variance for the confidence interval calculation will come from an Analysis of Variance of the Test and Reference results using a statistical model containing terms for Treatment and Site.

For the proportion of subjects with clinical success, the Test treatment will be considered to be therapeutically equivalent to the Reference treatment if the 90% confidence interval on the difference between Test and the Reference proportions is contained within the interval -20% to +20%. The confidence interval will be constructed using Wald's method with Yates' continuity correction.

Therapeutic equivalent evaluations in the per-protocol (PP) population will be considered definitive and those in the mITT will be considered supportive.

Superiority

For the percent reductions from baseline in the inflammatory and non-inflammatory lesion counts, each active treatment will be evaluated to determine if it has superior efficacy to that of the Vehicle at Visit 4/Week 12 via an Analysis of Variance using a statistical model containing terms for Treatment and Site.

The proportion of subjects with clinical success for each active treatment will be compared to that of the Vehicle using a Z-test with Yates' continuity correction.

All hypothesis tests will be two-sided at a significance level of $\alpha = 0.05$, except confidence intervals which will be based on $\alpha = 0.1$ (i.e. 90% coverage). Superiority analyses in the mITT population will be considered definitive and those in the PP will be considered supportive

8.1.5 Safety and Adverse Events Analysis

The frequency and percent of subjects with adverse events will be summarized by MedDRA system organ class and preferred term and by severity and relationship to study drug for all three treatment groups. [REDACTED]

[REDACTED]. The comparable safety of the Test and Reference treatments will be evaluated by statistical comparison of the proportion of subjects who reported any adverse events. The frequency and distribution of application site reactions of erythema, dryness, scaling/peeling, burning/stinging, erosion, edema, pain and itching will be summarized and compared descriptively. Safety comparisons will be performed only for the safety intent-to-treat population.

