Study Visits:	
Clinical Evaluations will be performed at:
 
 1. Visit 1/Day 1 (Baseline) 2. Visit 2/Week 4/Day 28 (± 4 days)(Interim) 3. Visit 3/Week 8/Day 56 (± 4 days)(Interim) 4. Visit 4/Week 12/Day 84 (± 4 days)(End of treatment/End study) 
Safety will be assessed by monitoring adverse events at each visit and at the

Protocol No: PRG-NY-15-003

	Week 2/Day 15 (± 4 days) Telephone Contact.
Evaluations:	The number of facial inflammatory and non-inflammatory lesions as well as the Investigator's Global Assessment (IGA) will be recorded at baseline and all subsequent visits.
Endpoints:	
The two primary efficacy endpoints will be the:
 
1) Mean percent change from baseline to Week 12 (Day 84) in the inflammatory (papules and pustules) lesion count and2) Mean percent change from baseline to Week 12 (Day 84) in the non-inflammatory (open and closed comedones) lesion count. 
The secondary endpoint will be the proportion of subjects at Week 12 with a clinical response of "success", defined as an IGA score that is at least 2 grades less than the baseline assessment.

Safety:	The incidence of all adverse events reported during the study will be summarized by treatment group. Equivalence of the test and reference with regard to safety will be evaluated by comparing the nature, severity and frequency of their adverse event profiles. In addition, the test and reference treatments' frequency and distribution of application site reactions of erythema, dryness, scaling/peeling, burning/stinging, erosion, edema, pain and itching will be summarized and compared descriptively.

ABBREVIATIONS

AE	Adverse Event
ANOVA	Analysis of Variance
CMH	Cochran–Mantel–Haenszel test
CRF	Case Report Form
DCF	Data Correction Form
FDA	US Food and Drug Administration
GCP	Good Clinical Practices
ICH	International Conference on Harmonization
IGA	Investigator's Global Assessment
IRB	Institutional Review Board
ITT	Intent- to-treat (population)
IU	International Unit
IUD	Intra-Uterine Device
LOCF	Last Observation Carried Forward
MedDRA	Medical Dictionary for Regulatory Activities
miITT	Modified Intent-to-Treat (population)
NSAID	Non-Steroidal Anti-Inflammatory Drug
OTC	Over the counter
PI	Principal Investigator
PP	Per- protocol (population)
Rx	Prescription
SAE	Serious Adverse Event
SAP	Statistical Analysis Plan
SPF	Sun Protection Factor
Sub-I	Sub-Investigator
UPT	Urine Pregnancy Test

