2.2 Safety

Safety of the test and reference products will be compared by evaluating the nature, severity and frequency of their adverse event profiles. All adverse events that occur during the study will be recorded. Descriptions of reactions or complaints will include the approximate date of onset, the date the adverse event ended, the severity of the adverse event, and the outcome. Comparisons between the treatment groups will be made by tabulating the frequency of Subjects with one or more adverse events (classified into MedDRA terms) during the study. Pearson's Chi-Square test or Fisher's Exact test, whichever is most appropriate, will be used to compare the proportion of subjects in each treatment group with any adverse event. The adverse events reported by at least five percent of the subjects in any treatment group will be summarized descriptively.

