5.1 Methodological Considerations

The study will be conducted under the same protocol across all the sites. No formal statistical analyses are planned to evaluate the consistency of efficacy results across the multiple clinical sites. These results, however, will be tabulated and if a site's efficacy data are obviously inconsistent with the results across all sites, this will be explored and addressed in the final study report.

Two-sided hypothesis testing will be conducted for all the tests. Resulting p-values less than 0.05 will be considered statistically significant unless noted otherwise. No adjustments of p-values for multiple comparisons will be made. No interim analyses are planned. SAS software will be used for all data analyses and tabulations.

5.2

[REDACTED]

[REDACTED]

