5.6 Safety Variables and Analyses

Duration of Treatment and Medication Compliance

Number of applications, days of exposure, and compliance rate will be summarized by treatment group using descriptive statistics. For each subject, the overall duration of treatment (days) will be calculated using the following formula:

$$\text{(Date of last application of study medication)} - \text{(Date of first application of study medication)} + 1.$$

Medication compliance rate (%) will be calculated for each subject as follows:

$$\text{(Total number of applications used)} / \text{(Expected number of applications)} *100\%.$$

Adverse Events

Adverse events (AEs) will be coded in MedDRA, version 15.1. Treatment-Emergent Adverse Event (TEAE) is defined as any AE occurs on or after applying the first dose of study drug. Number and percent of subjects reporting TEAEs will be tabulated by treatment group. Summaries will be presented by body system and preferred term for the ITT population. Similar tables will be presented by severity and relationship to study drug. TEAEs reported by more than 5% subjects for any treatment group will also be summarized. In summaries of incidence rates (frequencies and percentages), severity and relationship to study drug, subjects who report more than one event that are mapped to the same preferred term will be counted only once under the strongest severity and relationship, accordingly. The difference between Test and Reference treatments with regard to the severity and frequency of their dermatological adverse events will be statistically evaluated. Fisher's exact test will be used to compare the proportions of subjects of the two active treatment groups who report any TEAE.

Treatment-Emergent Serious Adverse Events (TESAEs) and TEAEs that led to treatment interruption or discontinuation will be presented in [data listings](#).

Concomitant Medications

Concomitant medications will be coded using the WHO Drug Dictionary, version September, 2014, and will be presented in [data listings](#).

Application Site Reactions

Frequency and distribution of application site reactions of erythema, dryness, scaling/peeling, burning/stinging, erosion, edema, pain and itching will be summarized and compared descriptively by visit.

Safety comparisons will be performed only for the ITT population.

6 Appendices

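### Comparable safety of Test and Reference rests on a test of no difference in any-AE rates, with no visible interval or margin, so a non-significant result would not support it

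*Protocol*

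**What the plan says.** The protocol synopsis, under Safety, sets the aim: "Equivalence of the test and reference with regard to safety will be evaluated by comparing the nature, severity and frequency of their adverse event profiles". Protocol 8.1.5 turns this into an analysis: "The comparable safety of the Test and Reference treatments will be evaluated by statistical comparison of the proportion of subjects" reporting any adverse event.

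The method is a test of no difference. Protocol 2.2, on the any-AE outcome, has: "Pearson's Chi-Square test or Fisher's Exact test, whichever is most appropriate, will be used to compare the proportion of subjects in each treatment group". SAP 5.6 narrows it to the two active arms: "Fisher's exact test will be used to compare the proportions of subjects of the two active treatment groups who report any TEAE". SAP 5.1 adds "Two-sided hypothesis testing will be conducted for all the tests" and "Resulting p-values less than 0.05 will be considered statistically significant unless noted otherwise".

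Other safety comparisons are planned. TEAEs are tabulated by system organ class and preferred term, severity and relationship. SAP 5.6 promises a statistical evaluation of the severity and frequency of dermatological events, Test against Reference, without naming a method. Application site reactions are compared descriptively by visit.

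For efficacy, the plan states equivalence rules. IGA success needs a 90% interval for the difference in proportions inside -20% to +20% (Protocol 8.1.4, SAP 5.5.2). Each lesion count needs a 90% Fieller interval for the ratio of means inside 0.80 to 1.25. No counterpart for adverse events is visible.

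**The concern.** In SAP 5.5.1 the equivalence null hypothesis is that the products differ by at least the margin, so only adequate precision can reject it. In the safety analysis the null is equality. Imprecision then works in favour of the wanted conclusion: the fewer the subjects or events, the more likely a non-significant p-value, whatever the truth.

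Comparing safety profiles is part of the stated study objective. If the any-AE test is non-significant, the report will have a p-value beside the words comparable safety, and nothing to show how large an excess with the generic remains compatible with the data. Primary efficacy conclusions are not affected.

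**Working it through.** **Is there a plan figure to reproduce?** No. The visible text gives no power, arm size or overall AE rate for the safety comparison. The sample sizes are redacted, and Protocol section 7 gives only single-event rates (0.4% each). The main point follows from the form of the test and needs no numbers. The figures below only show its size.

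**Assumed inputs.** Test and Reference allocated 1:1; 150 to 500 subjects per active arm; true Reference any-AE rate of 5%, 10%, 20% or 30%; true excess with Test of 3, 5 or 10 percentage points. From the documents: Fisher's exact test, two-sided, significant if p < 0.05.

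**Power formula.** Power = Σ Bin(x; n, p_T) · Bin(y; n, p_R), summed over all pairs (x, y) for which Fisher's two-sided p is below 0.05. This is exact, not simulated.

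**Results for a Reference rate of 10%:**

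| n per arm | no difference | +3 points | +5 points | +10 points |
|---|---|---|---|---|
| 200 | 3.4% | 12% | 28% | 77% |
| 300 | 3.6% | 18% | 41% | 92% |
| 400 | 3.8% | 23% | 53% | 97.5% |
| 500 | 3.9% | 28% | 63% | 99% |

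**Over all 20 combinations** of five arm sizes (150, 200, 300, 400, 500) and four Reference rates:

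- +3 points: power 7% to 44%, below 50% in 20 of 20.
- +5 points: power 12.5% to 83%, below 50% in 15 of 20.
- +10 points: power 39% to over 99%, below 50% in 2 of 20, both at 150 per arm.

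**What a non-significant result tells the reader.** Take n = 300 and a Reference rate of 10%. With equal true rates the test is non-significant with probability 1 − 0.036 = 0.964. With a true 5-point excess the probability is 1 − 0.411 = 0.589. The ratio is 0.964 / 0.589 = 1.6, so non-significance barely separates the two situations.

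**A worked outcome.** Suppose 45/300 (15%) on Test and 30/300 (10%) on Reference.

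- Fisher's two-sided p = 0.083, not significant.
- Difference = 0.15 − 0.10 = 0.05.
- SE = √(0.15 × 0.85/300 + 0.10 × 0.90/300) = √0.000725 = 0.0269.
- Wald 95% interval: 5.0 ± 1.960 × 2.69 = −0.3 to +10.3 points. The Newcombe interval agrees to 0.1 point.
- Wald 90% interval: 5.0 ± 1.645 × 2.69 = +0.6 to +9.4 points.

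The p-value alone would be reported as no significant difference. The 95% interval shows that an excess of 10 points is not excluded, and the 90% interval excludes zero. The choice of level changes the reading, so it has to be fixed in advance.

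**What an interval would deliver.** With equal true rates of 10% and n = 300, the 90% half-width is 1.645 × √(2 × 0.10 × 0.90/300) = 4.0 points. Over the assumed grid it runs from 2.3 points (n = 500, rate 5%) to 8.7 points (n = 150, rate 30%).

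**The case against.** The strongest reply is that no decision rule is written. Where the plan wants one, it states the condition for equivalence explicitly. For safety it does not, and SAP 5.6 speaks only of comparing proportions. That stands: a reader might infer that p > 0.05 will be declared proof of comparable safety, but neither document says so. What remains is that Protocol 8.1.5 names this comparison as the means of evaluating comparable safety, and the test named yields a p-value and no estimate of the difference.

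A reader might also infer that the test would mostly miss a real excess. The documents cannot support that without arm sizes, an AE rate and a stated excess. On the assumptions above it holds for about 3 points, often holds for 5, and fails for 10 points at 200 or more per arm. Nor do the documents say what excess would matter clinically.

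The any-AE test is not the whole safety assessment. Severity, relationship, dermatological events and site reactions are all examined, so it would be wrong to say that safety goes unassessed. But none of these visibly provides an interval for the Test-Reference difference, and the dermatological method is not named.

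Text just before the key sentence in Protocol 8.1.5 is redacted and could bear on this, so the accurate statement is that no interval is visible. SAP 5.6, the detailed safety section, shows no redaction and contains none.

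Finally, counts by arm are tabulated, so anyone can compute an interval afterwards. True, but then its method and level are chosen after the data are seen.

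**Conclusion.** The concern holds in a limited form. The plan attaches comparable, or in the synopsis equivalent, safety to a test of no difference. Non-significance of that test cannot support the claim, and no interval or margin for the AE difference is visible. This conclusion does not depend on any redacted figure.

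Its practical size does. With an assumed 10% Reference rate, a 5-point excess would be non-significant in about 72% of trials at 200 per arm, falling to about 37% at 500. A 10-point excess would be non-significant in about 23% and 1% respectively. The plan's own handling of IGA success shows that interval-based reasoning for a proportion is already in use. The change is worth making because comparing safety is a stated objective and the better method costs almost nothing.

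**What to change.** In SAP 5.6 and Protocol 8.1.5:

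1. Base the comparable-safety statement on the Test-minus-Reference risk difference with a Newcombe or Miettinen-Nurminen confidence interval, for any TEAE and for skin-related TEAEs (SAP Table 14.3.2.5 already covers the latter).
2. State the level in advance: 95%, or 90% to match the convention for confidence intervals in Protocol 8.1.4.
3. Keep Fisher's test as descriptive, and state that a non-significant result will not be read as evidence of comparability.
4. In the protocol synopsis, replace the equivalence wording for safety with a statement that safety will be compared, because no safety margin is set. Without a margin the interval shows what excess is not excluded; it does not establish equivalence either.

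The cost is SAP and protocol wording and one extra column in the AE tables, with no new data, subjects or procedures. The downside is that the safety statement may read less favourably, because the interval shows how much excess the trial cannot rule out.

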8.2 Comparability of Subjects at Baseline

The statistical significance of any treatment group difference in the distribution of categorical variables such as gender will be tested using Cochran–Mantel–Haenszel (CMH) test for general association adjusted for site. Continuous variables, such as age, will be analyzed using a two-way analysis of variance (ANOVA) model with site and treatment as a fixed effect.

9. CONSENT/ASSENT CONSIDERATIONS AND PROCEDURES

It will be made clear to the subject that, for the purposes of the study, they are consenting only for topical application of medication or vehicle. Investigators may discuss the availability of the study and the possibility for entry with a potential subject without first obtaining consent/assent. However, informed consent/assent must be obtained and documented prior to initiation of any procedures that are performed solely for the purpose of determining eligibility for research, including withdrawal from current medication(s). When this is done in anticipation of, or in preparation for, the research, it is considered to be part of the research.

The study must be approved in writing by an appropriate IRB as defined by FDA regulations. A copy of the Letter of Approval from the IRB, which also contains specific identification of the documents approved, must be received by Perrigo, prior to study commencement.

Periodic status reports must be submitted to the IRB at least annually as required by the site's IRB, as well as notification of completion of the study and a final report within three months of study completion or termination. A copy of all reports submitted to the IRB must be sent to Perrigo.

The investigator(s) has both ethical and legal responsibility to ensure that each subject being considered for inclusion in this study is given a full explanation of the protocol. This shall be documented on a written informed consent/assent form, which shall be approved by the same Institutional Review Board (IRB) responsible for approval of this protocol. Each informed consent/assent form shall include the elements required by FDA regulations in 21 CFR Part 50. The investigator agrees to obtain approval from Perrigo of any written informed consent/assent form used in the study, preferably prior to submission to the IRB.

Once the appropriate essential information has been provided to the subject and fully explained by the investigators (or a qualified designee) and it is felt that the subject understands the implications of participating, the IRB-approved written informed consent/assent form shall be signed by the subject (or their parent/legally authorized representative) and the person obtaining consent/assent (investigator or designee). The subject shall be given a copy of the signed informed consent/assent form and the investigator shall keep the original on file.

If the subject fails to meet the inclusion/exclusion criteria at the conclusion of the screening phase, the subject will be withdrawn from screening. In the event that the subject is re-screened for study participation, a new informed consent/assent form must be signed.

9.1 Subject Confidentiality

All participants are concerned for the individual subject's privacy and, therefore, all subject data will be identified only by a subject identification number and subject initials. However, in compliance with federal guidelines regarding the monitoring of clinical studies and in fulfillment of his/her obligations to Perrigo, it is required that the investigator permit the study monitor, any Perrigo authorized representative, and/or FDA representative to review that portion of the subject's medical record that is directly related to the study. This shall include all study relevant documentation including subject medical histories to verify eligibility, laboratory test result reports

Protocol No: PRG-NY-15-003

to verify transcription accuracy, admission/discharge summaries for hospital stays occurring while the subject is enrolled in the study and autopsy reports for deaths occurring during the study.

As part of the required content of informed consent, the subject must be informed that his/her medical chart may be reviewed by Perrigo or their authorized representative, or a representative of the FDA. Should access to the medical record require a separate waiver or authorization, it is the investigator's responsibility to obtain such permission from the subject in writing before the subject is entered into the study.

To preserve the subject's confidentiality, the data collected will be available only to the investigators of the study, their support staff, Perrigo or their authorized representative and possibly the FDA.

All reports and communications relating to the subject in the study will identify each subject only by the subject's initials and by the subject number. The investigator agrees to furnish Perrigo with complete subject identification, if necessary on a confidential follow-up form, which will be used for the purpose of a long-term follow-up, if needed. This will be treated with strict adherence to professional standards of confidentiality and will be filed at Perrigo under adequate security and restricted accessibility.

